7.1.4. Bleeding Episodes

If a subject experiences a bleeding event at any time during the study, he or his caregiver should follow the guidance for the treatment of bleeds, to be provided to each subject and/or caregiver. Guidance for study staff is provided in [Appendix A](#). The type of bleed and the dose required to stop the episode will be recorded in the subject's electronic patient diary (eDiary, EPD).

In this study, when a subject reports a bleed or hemorrhage, and is treated with study drug, it will be classified as either spontaneous or traumatic by the subject or the subject's caregiver. The subject's eDiary will serve as the source document for bleeding episodes while on the study.

In this study, a bleed will be defined as follows: a bleeding episode starts from the first sign of a bleed and ends no more than 72 hours after the last treatment for the bleed, within which any symptoms of bleeding at the same location, or injections less than or equal to 72 hours apart, are considered the same bleed. Any injection to treat the bleed, taken more than 72 hours after the preceding one, will be considered the first injection to treat a new bleed at the same location. Any bleeding at a different location is considered a separate bleed, regardless of time from last injection.

Spontaneous bleeding episodes: Bleeding episodes should be classified as spontaneous if a subject records a bleeding event when there is no known contributing factor such as definite trauma or antecedent strenuous activity. The determination of "strenuous" is at the discretion of the Investigator. Target joints can have spontaneous bleeding episodes.

Traumatic bleeding episodes: Bleeding episodes should be classified as traumatic if a subject records a bleeding event when there is a known or believed reason for the bleed. For example, if a subject were to exercise strenuously and then have a bleed, even in the absence of any obvious injury, the bleed would be recorded as a traumatic bleed. Target joint bleeding episodes can be traumatic if a known action led to bleeding into the joint.

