5.4 Electronic Patient Diary (EPD) Data/eCRF injections

Subject recorded diary data was originally queried via a defined process which required confirmation with the subject of **all** changes. Taking into consideration audit findings and industry standards to limit changes of subject reported data, the query process was updated to **only allow changes defined as not requiring subject confirmation**. Although consolidation of records of single vials recorded within 60 mins of each other (SVC/L60) was classified as a change not requiring subject confirmation (as agreed with MHRA in 2014), these changes are no longer being made directly into the data, but will be applied via a programmatic data convention. In addition, true duplicate records resulting from administrative issues and hence not requiring subject confirmation of the change will be deleted. These programming algorithms to address these two scenarios are described as follows:

1) Record consolidation:

When a dose requires more than one vial and these vials are erroneously recorded in the EPD/eCRF as separate injections, albeit within a short time window, the change to consolidate these multiple records into one record is called Single Vial Consolidation (SVC). Based on the EPD set up, the programming algorithm to identify and consolidate the records is as follows:

- Identify all injection records within 60 minutes of one another where the variables (injection date/times, lot numbers, number of vials, and vials strength in nominal IU) are not exactly the same on each record. There are three scenarios:
 - a) Date and time of injections **are not** exactly same, and lot numbers, number of vials, and vials strength in nominal IU **are not** the same.
 - b) Date and time of injections **are** exactly same, but lot numbers, number of vials, and vials strength in nominal IU **are not** the same.
 - c) Date and time of injections **are not** exactly same, but lot numbers, number of vials, and vials strength in nominal IU **are** the same.
- Consolidate injections as follows:
 - Record with earliest injection date/time retained with corresponding contextual information
 - Combine/sum values related to the dose (e.g. lot numbers, number of vials, volume injected, nominal and actual dose) into the single retained record

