One exception to note: if injections identified with the above algorithm have distinctly different reasons (e.g. one injection is recorded as bleed or surgery and another is recorded as prophylaxis, additional, or OTHER), then the records should NOT be consolidated.

2) True duplicates removal:

When injections are identified in the EPD with exactly the same date/times, lot numbers, number of vials, and vials strength in nominal IU, due to the EPD set up, these must have resulted due to administrative issues and are therefore true duplicates. There are four types of administrative issues as follows:

- a) Technical transmission issue;
- b) Entry of same record into 2 different devices;
- c) Duplicate manual entries; and
- d) Records duplicated in EPD and eCRF, which although could be removed via the query process, still remain

The programming algorithm to identify and delete the duplicates is as follows:

- Identify all injections that have exactly the same date/times, reasons for injection, lot numbers, number of vials, and vials strength in nominal IU
- Remove the duplicates and keep a single record. However, if injections have distinct reasons, such as one injection that is recorded as prophylaxis and another has no reason recorded (blank), the injection with prophylaxis is kept.

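### SAP 5.4 merges or deletes bleed-treatment injection records without checking bleed location, so a second bleed site can drop out of the bleeding-rate endpoints

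*SAP*

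**What the plan says.** SAP 5.4 sets two programmed cleaning rules for injection records from the diary and eCRF.

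- **Consolidation.** The stated target is one dose that needed several vials, with the vials wrongly entered as separate injections. The instruction begins "Identify all injection records within 60 minutes of one another where the variables". Those variables are date/time, lot, vial count and vial strength, and the condition is that they are not all equal. For what survives, the SAP says "Record with earliest injection date/time retained with corresponding contextual information" and "Combine/sum values related to the dose (e.g. lot numbers, number of vials, volume injected, nominal and actual dose) into the single retained record". There is one exception: records stay apart "if injections identified with the above algorithm have distinctly different reasons", for example where "one injection is recorded as bleed or surgery and another is recorded as prophylaxis, additional, or OTHER".
- **Duplicate removal.** The instruction is "Identify all injections that have exactly the same date/times, reasons for injection, lot numbers, number of vials, and vials strength in nominal IU", after which one record is kept. The justification is that "due to the EPD set up, these must have resulted due to administrative issues and are therefore true duplicates".

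Protocol 7.1.4 defines the episode: "Any bleeding at a different location is considered a separate bleed, regardless of time from last injection". SAP 7.1.1 repeats this and adds three counting rules. Only treated bleeds enter the ABR. One episode recorded in several places counts once in the overall ABR. Several sub-locations of one category, such as two joints, count once for that category. Spontaneous joint bleeds are a secondary endpoint in their own right (SAP 2.2.2), and SAP 7.3.1 summarizes ABR by location.

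**The concern.** The cleaning rules decide how many injection records reach the bleed derivation in SAP 7.1.1, yet location, which that derivation uses to separate bleeds, plays no part in them. If two records for bleeds at different sites carry the same reason, the later record's location has nowhere to go: it is neither in the retained context nor among the summed fields. Because only treated bleeds count, a bleed whose injection record has been absorbed or deleted leaves the numerator.

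There is also a tension inside the SAP. The change-classification table in Section 9 treats an alteration of bleed location or bleed type as needing the subject's confirmation. The 5.4 convention can discard both without it.

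At stake are the spontaneous-joint and by-location ABR and, in some cases, the overall ABR. At this step the rules can remove bleeds but not add them, so any error runs downward.

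**Working it through.** The plan gives no figure on this point, so there is none to reproduce. The check has four steps.

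**1. Apply the 5.4 rules literally to pairs of records.** Vials here means lot, count and strength together.

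| Pair | Rule | Result |
|---|---|---|
| Spontaneous right knee; spontaneous left elbow 30 min later; different vials | Consolidation | One record, right knee |
| The same, identical vials | Consolidation | One record, right knee |
| The same two sites at the same time, different vials | Consolidation | One record; the times tie, so the rule does not say which site survives |
| The same two sites at the same time, identical vials | Duplicate removal | One record |
| Spontaneous at one site, traumatic at another 30 min later | Unsettled | Merged if both count as the reason bleed; kept apart if the types count as different reasons |
| Spontaneous and traumatic, same time, identical vials | Unsettled | If the types are different reasons, fits neither the three consolidation scenarios nor the duplicate key |
| Bleed and prophylaxis, 30 min apart | Exception | Both kept |
| Two spontaneous bleeds 61 min apart | Outside window | Both kept |

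All four same-reason pairs inside the window lose a location.

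**2. Compare with what SAP 7.1.1 would count.** Both records are spontaneous and the first site named is the one retained. Each cell shows the count due, then the count obtained.

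| Sites | Nature of the pair | Overall | Joint |
|---|---|---|---|
| Knee, elbow | Two episodes | 2, 1 | 2, 1 |
| Knee, elbow | One multi-location episode | 1, 1 | 1, 1 |
| Muscle, knee | Two episodes | 2, 1 | 1, 0 |
| Muscle, knee | One multi-location episode | 1, 1 | 1, 0 |

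The overall ABR is wrong only when the records are two episodes. The joint count is wrong then too, and it is also wrong for a single episode when the lost site is the only joint.

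**3. Size.** SAP 7.1.1 gives ABR = bleeds / T × 365.25, with T the days in the efficacy period. One lost bleed lowers the subject's ABR by 365.25/T:

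- T = 90: 365.25/90 = 4.06
- T = 182.625: 2.0
- T = 365.25: 1.0
- T = 730.5: 0.5
- T = 1461: 365.25/1461 = 0.25

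These T values are illustrative; four years is the stated limit on continuation. A group mean over N subjects moves by 365.25/(T × N). With T of one year and the planned numbers from the two parent studies, that is 1.0/20 = 0.05 (9HB02PED) or 1.0/100 = 0.01 (998HB102) per lost bleed. The regimen tables hold fewer subjects, so the shift there would be larger.

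**4. Would the sensitivity analysis show it?** Section 9 restores only changes that need subject confirmation. Its table does not code the combining of vials within 60 minutes that way; it leaves this to the 5.4 convention. The natural reading is that both analyses pass through the same convention and carry the same loss. The SAP's output list names no listing of records merged or deleted by program.

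**The case against.** The case against has weight. Consolidation is aimed at vials of one dose, and Protocol 7.1.4.2 tells subjects to treat a bleed with a single dose. Two vials 20 minutes apart may well be one dose for bleeding noted at two sites, and SAP 7.1.1 then wants one event in the overall ABR. The regulator agreed in 2014 that combining vials within 60 minutes needs no subject confirmation. The diary set-up, which the SAP invokes for both rules, may make some of these pairs impossible. It is not described, so this can be neither confirmed nor dismissed. ABR is secondary and descriptive, with no testing.

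Three stronger readings that a reader might infer are not supported:

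- **That every merge removes a whole bleed from the overall ABR.** This fails for a single multi-location episode.
- **That spontaneous/traumatic or follow-up/new-bleed pairs are certainly lost.** The exception is only illustrated. SAP 6.5 lists treatment of a bleeding episode as one reason, and Section 9 codes bleed type apart from injection reason. But SAP 7.1.1 and 7.4.1 label injections as spontaneous, traumatic or follow-up, and Section 9 mentions a change from new bleed to follow-up under injection reason. These pairs are ambiguous.
- **That matching vials alone trigger deletion.** The duplicate key also needs the same date/time, lot and reason. With matching vials at different times, consolidation applies.

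What the objection does not answer is the same-reason pair at different sites. The records' own locations may contradict the assumption of one wrongly split entry, and the algorithm never looks.

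**Conclusion.** The gap is real but narrow. As written, SAP 5.4 collapses two same-reason bleed-treatment records at different locations into one record with one location, in conflict with SAP 7.1.1 and Protocol 7.1.4. By-location and spontaneous-joint ABR can each lose a bleed. The overall ABR falls by 365.25/T for that subject only where the records are separate episodes.

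This rests on a literal reading of the two rules and on contextual information including bleed location and type, which the SAP does not define. How many such pairs exist is unknown. The number is probably low, because the rule is built for split entries of one dose. A reader might infer that the reported ABR is materially biased; nothing in the documents shows that. The point merits correction because the error runs one way, the planned re-run would not expose it, and the remedy is small.

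**What to change.** In SAP 5.4:

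1. Do not delete as a duplicate any bleed-treatment record whose bleed location differs from that of its match.
2. When bleed-treatment records with different locations are consolidated, sum the dose but carry forward every recorded location and type. Let SAP 7.1.1 decide whether they are separate bleeds or one multi-location episode.
3. State whether spontaneous, traumatic and follow-up count as different reasons for both rules, and which record is retained when times tie.
4. List all bleed-treatment records merged or deleted by the convention, with the location and type of each.

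A difference in bleed onset alone should not block consolidation. Two vials of one dose with onsets typed a few minutes apart would then stay split, which inflates injections per bleed and lowers dose per injection in SAP 7.4.1.

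The cost is one location check in the program, a few sentences in the SAP and one listing. If no such pairs exist, the listing shows that.

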6. STUDY SUBJECTS

6.1. Disposition of Subjects

Subject disposition will be summarized for study 9HB01EXT for subjects from each parent study and overall. This table will present the number of subjects in the All-enrolled Analysis Set, the number and percentage of subjects enrolled in the FAS including the number of subjects with an efficacy period, the number of subjects within each treatment regimen, the number and percentage of subjects in the Safety Analysis Set, and the number and percentage of subjects in the surgery subgroup. The number of subjects with the status of completed and discontinued from the study, including the primary reason for those who discontinued, will be tabulated. Subject disposition, including the date of the last visit and the reason for early termination for subjects who did not complete the study, will be provided in a data listing.

The number and percentage of enrolled subjects will be summarized by country, site, and treatment regimen using All-enrolled Analysis Set. The number of subjects attending each visit in study 9HB01EXT will be summarized overall by planned visit using the Safety Analysis Set. The summary for each study visit will include only those subjects for whom the visit evaluations reflect the designated visit on the study (i.e., including subjects for whom this visit represents the end-of-study visit due to early termination).

6.2. Demography and Baseline Disease Characteristics

Demographics and baseline disease characteristics will be summarized by study 9HB01EXT treatment regimen, surgery subgroup, and overall, using the Safety Analysis Set.

6.2.1. Demography

Demographic characteristics including age (years), geographic location, height (cm), weight (kg), and body mass index (BMI, kg/m^2) will be summarized using the data at entry into study 9HB01EXT. Race and ethnicity will also be included in the summary using the data at the entry into the parent study. Geographic locations are defined as Europe, North America, and other. For subjects from study 998HB102, Europe includes Belgium, Germany, France, United Kingdom, Italy, Poland, Russia, and Sweden. North America includes Canada and the United States. Other countries include Australia, Brazil, China, Hong Kong, India, Japan, and South Africa. For subjects from study 9HB02PED, Europe includes Ireland, the Netherlands, and the United Kingdom. North America includes the United States. Other countries include Australia, Hong Kong, India, and South Africa.

6.2.2. General Medical and Surgical History

An updated medical and surgical history is collected at the first visit of study 9HB01EXT. These updated records will be provided in the listing only. A summary of this updated medical and surgical history by body system by study 9HB01EXT treatment regimen, the surgery subgroup, and overall for the Safety Analysis Set will be presented. A subject will be counted only once if they reported one or more occurrences in the same body system.

6.2.3. Physical Examination

Physical examination continues to be performed annually in this extension study. A listing of subjects with an abnormal status will be presented.

6.3. Protocol Deviations

All protocol deviations will be recorded throughout study 9HB01EXT. Major and minor protocol deviations/violations are to be pre-specified prior to database lock. All major protocol deviations during study 9HB01EXT will be summarized by study 9HB01EXT treatment regimen, the surgery subgroup, and overall using the FAS. Protocol deviations that occurred during surgical/rehabilitation periods will be attributed to the surgery subgroup only. All deviations, both major and minor, will be provided in a data listing.

In addition, another set of protocol deviation (PDs) will be determined using the EPD dataset created for the impact analysis, where changes requiring subject confirmation have been reverted to the original pre-change state. Details specific to the impact analysis will be provided in Sections 9 below. This set of PDs will be summarized and listed in a similar manner to the primary set for the FAS.

6.4. Non-study Drug Medications

6.4.1. Concomitant Medications

Two listings will be provided, one for concomitant medications taken through the End of Study Visit/Early Termination Visit and the other for concomitant medications taken after the End of Study Visit/Early Termination Visit and prior to the Follow-up visit/phone call.

Concomitant medications will be summarized by treatment regimen in study 9HB01EXT, the surgery subgroup, and overall using for the Safety Analysis Set.

Concomitant medications are those administered on or after 9HB01EXT Study Day 1, or administered prior to 9HB01EXT Study Day 1 and ongoing at the start of 9HB01EXT Study Day 1. They will be characterized based on the start and end dates relative to 9HB01EXT Study Day 1. Medications reported for a subject will be classified as concomitant unless they can be excluded as such, as follows:

- Medications with a start date after the follow-up visit will not be considered concomitant.
- For partial dates, if a concomitant medication start day is missing then the medication will be assumed to be a concomitant medication unless the start month and/or year or medication stop date can be used to determine if a medication is concomitant, as follows.
 - If the concomitant medication start day is missing, but the month and year are before the start month and year of 9HB01EXT Study Day 1 and the concomitant medication stop date is before the date of 9HB01EXT Study Day 1, then the medication will not be classified as concomitant.

- If the day of the start date is missing and the month and year are after the month and year of 9HB01EXT Study Day 1, then the medication will be classed as concomitant.
- If the month of the start date is missing and the year is before the start year of 9HB01EXT Study Day 1 and the stop date is before the date of 9HB01EXT Study Day 1, then the medication will not be classified as concomitant.

Concomitant medications will be coded using World Health Organization drug enhanced dictionary version March 2011.

6.4.2. Other Therapies and Procedures

Other therapies administered and concomitant procedures performed in study 9HB01EXT will be summarized by study 9HB01EXT treatment regimen, the surgery subgroup, and overall using for the Safety Analysis Set. The data will be listed.

6.5. Study Drug

Study treatment regimens are described in Section 3.2. The listing of all study drug administered will include the reason for administration (prophylaxis [regular or additional], treatment of a bleeding episode, surgery, other). Subject-level information on dosing with study drug will also be provided in a data listing.

Treatment with study drug (exposure, prophylactic dose, prophylactic dosing interval, and consumption) will be summarized by treatment regimen in 9HB01EXT using the FAS.

6.5.1. Exposure

6.5.1.1. Duration of rFIXFc Dosing, Number of Injections and Exposure Days to rFIXFc

The summary of exposure will be produced. Details of the summary are described in Section 7.3.2.

6.5.1.2. Last Prescribed Dose and Dosing Frequency

Subjects' last prescribed dose and dosing frequency will be summarized as a cross tabulation of dosing frequency by dose (IU/kg) in which the number and percentage of subjects who were last prescribed each combination of dose and dosing frequency (i.e., twice weekly or once every 5-6 days, 7 days, 8-13 days, ≥ 14 days) will be tabulated. A summary table will be provided for the overall prophylaxis regimen consisting of the individualized prophylaxis and weekly prophylaxis regimens in study 9HB01EXT for subjects from study 998HB102 overall and by age cohort for subjects from study 9HB02PED. The last prescribed dose will also be summarized for each dosing frequency using descriptive statistics. If no dose (dosing frequency) changes were prescribed, then a subject's starting dose (dosing frequency) will be used. The dose for the twice weekly regimen will be the average of the two doses given. Percentages will be based on the number of subjects in each prophylactic regimen (i.e., not on the number of subjects in each dosing frequency category).

6.5.2. Change of Treatment Regimens

For the changes in treatment regimens in study 9HB01EXT described in Section 5.3.1, the number of subjects with at least one treatment regimen change, the regimen first changed to, and the number of changes will be summarized by starting treatment regimen in study 9HB01EXT and overall.

6.5.3. Prophylactic Dose (IU/kg) and Dosing Interval (days)

Because prophylactic dosing in study 9HB01EXT is based on variable doses and dosing intervals, the amount of rFIXFc received prophylactically will be summarized as an average weekly dose. Descriptive statistics will be provided using the FAS for each prophylactic regimen.

The average weekly prophylactic dose (IU/kg) and the prophylactic dosing interval will be based on prophylactic doses that are not separated by a bleeding episode. Data to be included in the calculations, specifically the prophylactic doses and the total duration of prophylaxis treatment, will come strictly from intervals representing 2 consecutive prophylactic doses (PR) during the efficacy period (see Section 5.3.2 for a description of the efficacy period). The sum of doses at PR_x and the sum of interval durations (PR_{x+1} minus PR_x) will be determined across all evaluable intervals of PR_x to PR_{x+1}. As such, when a bleeding episode is encountered, the interval stops at the prophylactic dose prior to the event and continues with the first prophylactic dose after the event. The last PR dose during a given treatment regimen will be the end of the last interval used for these calculations. The start and stop time of a treatment regimen and the calculation of total duration in that treatment regimen are described in Section 5.3.1. If a subject is treated in a given treatment regimen more than once during study 9HB01EXT, the sum of doses at PR_x, sum of days in PR intervals, sum of days in PR intervals, and number of PR intervals will be calculated across all durations in that treatment regimen before the average weekly prophylactic dose and dosing interval are calculated using the formula below.

$$\text{Average weekly prophylactic dose} = \frac{\text{Sum of doses at PR}_x}{\text{Sum of days in PR intervals}} \times 7$$

$$\text{Average prophylactic dosing interval} = \frac{\text{Sum of days in PR intervals}}{\text{Number of PR intervals}}$$

For the personalized prophylaxis regimen, additional injections administered will also be included in the average weekly prophylactic dose and average dosing interval calculations.

Prophylactic dosing will be further characterized by the number of prescribed changes in the dose and the number of prescribed changes in the dosing interval while on a given prophylaxis treatment regimen. If both dose and dosing interval change, they will be included in each summary. Dose and dosing interval changes are based on recommendations made by the Investigator and may or may not reflect whatever modifications a subject actually made to his dosing regimen. The number of prescribed changes in the dose level and the number of prescribed changes in the dosing schedule will be summarized categorically (0, 1, 2, 3, 4, >4) and with descriptive statistics. If a subject is treated with a given treatment regimen more than

once during study 9HB01EXT, then the total number of changes will be across all durations in that treatment regimen.

